## GENERAL PROCEDURES

### Overview

The rest of the study manual from this point onward describes how participants who have been randomly assigned to one of the two study conditions (i.e., Control or SteadyRx) are handled throughout the main portion of the study (i.e., the post- randomization period). This section on general procedures covers procedures that are applied to all randomized participants, independent of their group assignment. The subsequent sections apply only to participants who have been assigned to the SteadyRx group. Thus, the focus of this section is on the monthly assessments.

### Monthly Assessments

**Reminder Calls.** Participants will be given reminder calls related to their scheduled monthly assessment by the student investigators. They will also receive follow up calls if they fail to show up for their scheduled appointment time. Reminder calls will be given one day before their scheduled appointment. The calls will be between 10AM – 6PM Monday through Thursday and 1PM – 5PM on Sunday.

If the participant does not answer, the student investigator will wait one hour and then call again. This process is repeated if they do not answer again. If they do not answer a third time, the student investigator will leave the following voicemail:

*“Hi (PERSON’s NAME), my name is \*First Name\* and I am calling on behalf of the SteadyRx research team. I just wanted to remind you that you have your monthly assessment scheduled for (APPOINTMENT TIME) tomorrow and confirm that you will be coming. Thank you and have a nice day.”*

If someone other than the participant answers the phone, follow the following script:

*“Hi, I’d like to speak to (PERSON’S NAME).” If the person on the phone asks who you are or why you are calling then say, “My name is \*First Name\* and I am calling to remind them about an appointment they have at Johns Hopkins tomorrow.” If they ask for further details tell them “I’m sorry, but I am only allowed to discuss details with (PERSON’S NAME).”*

Once the participant is one the phone, follow the following script:

*“Hi (PERSON’S NAME), my name is \*First Name\* and I am calling on behalf of the SteadyRx research team. I just wanted to remind you that you have a monthly assessment scheduled for (APPOINTMENT TIME) tomorrow and confirm that you will be coming.” If they say yes, say “Okay, great, remember that your appointment is at (APPOINTMENT TIME) and that you need to*

*bring your pill bottle and will be paid \$30 for completing the interview and you will receive an additional \$20 for bringing your pill bottle. That means you will be paid up to \$50 tomorrow for bringing your pill bottle and completing the interview."Once they respond, then say "Okay, see you at (APPOINTMENT TIME) tomorrow, have a great day, Bye."*

If they indicate that they are unsure, or do not know what you are talking about, follow the following script:

*"[name] asked me to call you because you are scheduled to come in for your monthly assessment interview tomorrow for the SteadyRx research study you are participating in."*

Reminder calls will be discontinued immediately upon request of the participant, will not exceed three per week, and will be discontinued after one month from the originally scheduled intake interview or appointment time.

**Collection Schedule.** Scheduling monthly assessments is the responsibility of the outreach coordinator and the student investigators in Kalamazoo. Both are responsible for different aspects of the monthly assessment protocol. Monthly assessments should be scheduled to occur every 30 days over the course of 180 days (for a total of six monthly assessments after random assignment). The first monthly assessment is scheduled for 30 days after the day of random assignment. During the Monthly Assessment Interview, the outreach coordinator should review and update the [Monthly Assessment Checklist-Outreach Coordinator](#), and the student investigator should update the [Monthly Assessment Checklist-WMU staff](#). The outreach coordinator should keep a record of all scheduled assessments, which should include their PTID, the scheduled date for all assessments, whether or not the assessment was collected for all planned assessments to date, the date that each collected assessment was actually conducted, the number of days that passed between the planned collection date and the actual collection date, and summary data indicating the overall percentage of planned assessments that have been collected to date and the average days from planned collection to actual collection for all collected assessments to date.

**Contacting No-Shows.** The student investigators are responsible for contacting participants who do not show up for monthly assessments. Any participant who does not show up for a monthly assessment at their scheduled time should be contacted via phone by student investigators reminded of their appointment, reminded of the \$50 they can earn, and rescheduled if necessary. Participants can also be contacted by using the information on the participant contact information sheet that was completed as part of the intake or most recent monthly assessment. Any updates that occur to the contact information should be noted on the most recent contact sheet. If necessary and if time allows, then the outreach coordinator can travel to the participant's residence to conduct the monthly assessment. A

record of all attempts to call no-shows should be kept on a separate log.

**Elements of the monthly assessments.** The outreach coordinator will be responsible for:

- Attaching the MEMS reader to the assessment computer
- Obtaining CD4 and HIV-1 RNA levels from medical record
- Scheduling the next monthly assessment

**Reading a participant's MEMS cap.** Upon a participant's arrival, the outreach coordinator will place the MEMS cap on the reader and initiate the reading.

Tutorials for reading a MEMS cap will be made available to the outreach coordinator from the student investigators as well as from the help section located within the database. They will obtain CD4 and HIV-1 RNA levels from the medical record or from printed labs given by the participants. The outreach coordinator will inform WMU staff of the participant's arrival and any new lab information.

**Conducting Monthly Assessments.** The remainder of the monthly assessment will take place over the phone with one of the student investigators located in Kalamazoo. The student investigator is responsible for reading each assessment question aloud to the participant and filling in the answers accordingly. Upon the completion of both the MEMS reading and phone assessments, the participant should be paid \$50. If the participant brought in recent CD4 and RNA lab readings and have an undetectable viral load, they should be paid \$100, up to twice during the study. All relevant data logs should be updated (see [Monthly Assessment Checklist – WMU Staff](#)).

The student investigator is solely responsible for conducting the following assessments:

- [Visual Analog Scale for self-reporting ART adherence](#)
- [Medical Outcomes Study HIV Health Survey](#)
- [Addiction Severity Index-Lite](#)
- [Patient Reactions Assessment](#)

In addition to the previous assessments, student investigators are also responsible for conducting the following assessments for participants in the SteadyRx group:

- [SteadyRx Satisfaction Questionnaire](#)
- [Software Usability Measurement Inventory](#)

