[name], and give the answers to the stratification variables. The principal investigator will then run the urn randomization procedure and relay the group assignment to the student investigator. The participant will then complete the rest of the surveys (Visual Analog Scale for self-reporting ART adherence, MOS-HIV, Patient Reactions Assessment, SteadyRx Reminder Enrollment Form, and Contact Information Sheet).

**Notifying Outreach Coordinator.** After the participant has been randomized and is completing the rest of the assessments (see above), the student investigator will inform the Outreach Coordinator of the group assignment. The Outreach Coordinator will bring the necessary materials to complete the intake to the participant (MEMS cap, CT Payer card, and smartphone (if in SteadyRx group). After the Outreach Coordinator is notified of study condition, and the assessments are finished, the student investigator will inform the participant of study condition.

**Notifying Participant of Study Condition.** The student investigator will notify the participant of the result of the randomization procedure.

If the result is the SteadyRx group, the student investigator will say the following:

“You have been assigned to the SteadyRx group. This means that you are able to be paid \$30 each month for coming here and completing an interview with our outreach staff. This also means that you will be provided with a cell phone for 6 months. You will be provided with a medicine cap that will go on top of your prescription HIV medication bottle. You are responsible for keeping track of both of these items. If either of these items are lost, stolen, or sold, you will be penalized. If you keep your cell phone for the whole study, you will receive \$100 at the end of the study. Instead of receiving \$100 for returning the cellphone, you may choose to keep it. Each time you bring your medicine cap back to an interview, you will receive \$20. On the cell phone, you will find an app called SteadyRx, which we will teach you how to use now. Do you have any questions?”

If the result is the control group, then the student investigator will say the following:

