### Assessing Videos in SteadyRx

The responsibility of assessing the videos submitted by participants to PillWatch will be the student investigators' in Kalamazoo. Videos will be assessed once per day for all participants by one of the student investigators. The student investigators will create a schedule to equally share this task over the course of the entire study. The student investigators will only use the computers whose IP addresses have been approved by the CTPayer system.

The student investigators will then login using the admin account used to create SteadyRx participants' Motiv8 accounts. Then the student investigators will navigate to the videos tab. All videos marked as unattended should be attended to and then either approved or rejected according to the criteria in the PillWatch training module.

Two of the student investigators will assess each video independently. They will be assigned to be the first or the second appraiser. A schedule has been created in order to split this responsibility evenly. The first appraiser will input their decision in the first appraiser's google sheet in the study google drive. They will then notify the second appraiser that they have done so. The second appraiser will then input their decision in the second appraiser's google sheet. This will automatically update the first appraiser's google sheet. The second appraiser will then open the first appraiser's google sheet to check for agreement. If there is agreement, the second appraiser will log in to the Motiv8 systems website and either accept or reject the video submission. If there is not agreement, the second appraiser contacts the first appraiser to deliberate whether or not to accept or reject the video. If they are unable to reach agreement, they ask the third student investigator to independently review the video submission. The team will either accept or reject the video according to the third student investigator's decision.

The first week that the participant is in the study will be considered a training week. During this time, video submissions will be reviewed by the student investigators, who will provide feedback to the participant to insure that they are submitting videos that meet all of the criteria specified in the PillWatch protocol.

Once all videos have either been approved or rejected, the client's account will automatically update with the \$2 credit for one day of full medication

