## **SteadyRx Video Submission Feedback**

All participants in the SteadyRx group will obtain feedback on their video submissions. The level and detail of feedback is determined by how close the video submissions are to meeting all criteria for acceptance.

**Week One Training.** Participants will be instructed that the first week of participation is a training week, during which videos may be accepted that do not meet all criteria. Participants will receive feedback the day after their first submission, and every other day after the first submission until the end of training week. Feedback will be given by a student investigator calling the smartphone given to them for the study. Student investigators are to identify specific inadequacies in the submissions (e.g., not opening the pill bottle on screen), explain them to the participant, and check for understanding.

**Retraining.** If, after feedback has been delivered twice and there has been no improvement, the student investigator will contact the Outreach Coordinator to schedule an appointment for the participant to come in for retraining. At the appointment, the Outreach Coordinator will go through the training materials and instruct the participant on submitting a video that meets all criteria for acceptance. Participants will be compensated \$20 for returning to Johns Hopkins for retraining.

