## **Data Management**

Data management is the responsibility of the student investigators and the outreach coordinator. The key outcome measures are all recorded automatically and electronically. This includes pill bottle openings and SteadyRx use measures. All participants will be trained to the point of skill mastery on all aspects of using the electronic pill bottles and the SteadyRx system. The data for all ACASI assessments will be stored in the Qualtrics database. The data for all MEMS caps readings will be stored within the medAmigo database. The data for all PillWatch

assessments will be stored in the backend of the SteadyRx application. All data will be stored on the SteadyRX server. With respect to the SteadyRX system servers, these Servers have been hardened against attack over the network and an intrusion detection system is in place. Administrative access to servers is by encrypted, private key-secured channels only. Servers are physically secured in a locked cabinet in a locked room in a secure facility accessible by photo ID only. The computer services provided under this project include daily system-wide on-site and encrypted offsite backups with incremental database backups in 15 minute intervals. All data transfer will be encrypted using 256-bit SSL encryption, the standard level of encryption used to secure eCommerce and banking transactions on the Internet. HIV serostatus and viral load measures, and drug use history will be provided by the participants' doctor and transmitted over the phone by the outreach coordinator to the WMU staff. A log of the materials assigned to the participants and a discharge log will also be kept on Google Drive.

All video submission data from those in the SteadyRx group will be recorded on individual google sheets. Submissions (y/n), time of submission, submission acceptances, money earned and when payments are made are included in the Google Sheets. Videos are independently accepted or rejected by two student investigators (see [Assessing Videos in SteadyRx](#)).

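### Monthly self-reports are read aloud and recorded by staff who know the allocation and coach only the SteadyRx arm, while an ACASI reference elsewhere names no instrument or visit

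*Combined protocol and SAP*

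**What the plan says.** Conducting Monthly Assessments (under Monthly Assessments) makes the follow-up visit largely a telephone interview: "The remainder of the monthly assessment will take place over the phone with one of the student investigators located in Kalamazoo". On that call, "The student investigator is responsible for reading each assessment question aloud to the participant and filling in the answers accordingly". For both arms the list headed "The student investigator is solely responsible for conducting the following assessments" contains the adherence Visual Analog Scale (VAS), MOS-HIV, ASI-Lite and the Patient Reactions Assessment. For one arm there is an addition: "student investigators are also responsible for conducting the following assessments for participants in the SteadyRx group", namely the satisfaction questionnaire and SUMI.

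The same staff role knows the allocation. The randomization procedures state: "The student investigator will notify the participant of the result of the randomization procedure". It also delivers much of the intervention. Under Assessing Videos in SteadyRx, "Two of the student investigators will assess each video independently". Under SteadyRx Video Submission Feedback, "Feedback will be given by a student investigator calling the smartphone given to them for the study". The CT Payer paragraph gives student investigators, with the principal investigator, the job of paying participants. The text supplied describes no blinded or independent assessor.

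Data Management says: "The data for all ACASI assessments will be stored in the Qualtrics database". It does not name the instruments or visits concerned.

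**The concern.** ACASI is a self-interview mode: the participant hears or reads the question and enters the answer without an interviewer. A telephone interview in which staff read the items and type the replies is a different mode. As written, a reader cannot tell how each self-report outcome was obtained.

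The mode matters because of who the interviewers are. SteadyRx participants describe their adherence and drug use to members of the team that accepts or rejects their dosing videos and coaches them. Controls have no video-review or coaching relationship with that team. The interviewer knows the arm when entering the answer. Either side of the call could shift the answers, and the shift need not be equal in the two arms. Self-reported adherence is a named secondary outcome, and drug-use days and MOS-HIV are exploratory. The Patient Reactions Assessment is meant to show whether the app's consult element changes perceived communication with the provider. All four are collected in both arms, so a shift that differs by arm would distort a comparison between them.

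**Working it through.** **1. Mode and staffing.** The documents state no bias and no power figure, so there is nothing to reproduce. The check is first a comparison of sections.

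| Question | What the documents give | Section |
|---|---|---|
| Who asks and records at follow-up? | Student investigator, by phone | Monthly Assessments |
| Do they know the arm? | Yes, they receive and announce it | Random Assignment, Procedures |
| What do they do only in the SteadyRx arm? | Account set-up, video decisions, bonus credits, feedback calls | CT Payer; SteadyRx procedures |
| What do they do in both arms? | Reminder and no-show calls, interviews, payment | Monthly Assessments; CT Payer |
| How large is the pool? | Apparently small: a third student investigator settles disagreements on videos | Assessing Videos in SteadyRx |
| What does ACASI cover? | Not stated | Data Management |

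**2. Intake.** The Procedures section has the participant completing the ASI-Lite and TOFHLA while the student investigator telephones the coordinator, but it also speaks of the ASI-Lite being administered. ACASI may therefore refer to intake. If it does, the mode changes between baseline and follow-up in both arms, and the MOS-HIV model adjusts for a baseline collected differently.

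**3. Which outcomes can be biased between arms?** The VAS, drug-use days, MOS-HIV and Patient Reactions Assessment can, because they are taken in both arms. The satisfaction form and SUMI cannot: they are given in one arm, and the analytic plan summarises acceptability descriptively. MEMS openings, viral load and app-usage logs do not come from this interview.

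**4. Illustration of size.** From the documents: N = 50, six monthly assessments, two-sided alpha 0.05. Assumed: 25 per arm, VAS SD 25 points, within-person correlation 0.5, no true effect, normal approximation.

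- SD of a six-visit mean = 25 × √((1 + 5 × 0.5)/6) = 19.1
- SE of the group difference = 19.1 × √(2/25) = 5.40
- False-positive rate for a differential b = Φ(b/SE − z) + Φ(−b/SE − z)

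At unadjusted 0.05, z = 1.96:
- b = 5: b/SE = 0.926, giving 0.1505 + 0.0020 = 0.152, about 15%
- b = 10: b/SE = 1.852, giving 0.457, about 46%

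The analytic plan says secondary p-values will be corrected but names no method. Assume Bonferroni over four secondary measures (MEMS percentage, self-report, CD4, RNA): alpha = 0.05/4 = 0.0125, z = 2.498.
- b = 5: 0.0580 + 0.0003 = 0.058, about 6%
- b = 10: 0.259, about 26%

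The same formula in SD units at unadjusted 0.05 gives this range:

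| Bias (SD) | One visit | Mean of six visits, correlation 0.5 |
|---|---|---|
| 0.1 | 6.4% | 7.5% |
| 0.2 | 10.9% | 15.2% |
| 0.3 | 18.6% | 28.4% |
| 0.5 | 42.4% | 63.9% |

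The 0.2 SD row for six visits is the 5-point case (5/25 = 0.2).

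**The case against.** The strongest reply is that the stakes are limited. The primary outcomes are MEMS and viral load, and self-reported adherence sits beside a MEMS version of the same measure, which serves as a check. That stands, and it makes this an improvement rather than a threat to the main result.

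Several stronger readings are tempting, and the documents do not support them.

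- **That the bias favours SteadyRx.** No payment depends on a VAS or ASI-Lite answer; incentives follow accepted videos and undetectable viral load. Participants who know that staff have seen their videos may over-report to please them, or may report more accurately than controls. The direction is open.
- **That these staff have no contact with controls.** They call, interview and pay both arms. Only the SteadyRx procedures, chiefly video review and coaching, are specific to one arm. Duties are shared across a pool, so the interviewer on a given call need not have judged that participant's videos.
- **That app satisfaction is differentially biased.** With one arm and a descriptive summary, there is no contrast to distort.
- **That Data Management already promises self-completed monthly forms.** It says only where ACASI data are kept.
- **That 15% and 46% are the trial's error rates.** They rest on assumed inputs and leave out the planned correction.

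A further objection is that self-completion may not be private. The intake section puts the assessment computer under remote control by the university team through TeamViewer, and no-show procedures allow visits at the participant's residence, where that computer is not available. Both points are fair, and the remedy has to deal with them. Participants will also know their arm whatever the mode, so self-completion reduces interviewer influence but does not remove reporting bias.

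**Conclusion.** The point holds in a limited form. The monthly interview mode and the ACASI reference are unreconciled. Four self-report measures compared across arms are collected by staff who know the allocation and who coach one arm only, so reporting or recording bias may differ by arm. Its direction and size cannot be established from the documents. Acceptability scores carry a separate risk of courtesy bias. The primary outcomes are untouched.

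That the interviewers are unblinded is inferred from their assigned duties; the text supplied does not use the word. The false-positive rates above show only that, with about 25 per arm, a modest differential could matter for a secondary comparison; even the corrected 6% compares with a nominal 1.25%. This is worth changing because the change is cheap, not because harm has been shown.

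**What to change.** State the mode of administration for each instrument at each visit, intake included, and bring Monthly Assessments and Data Management into agreement.

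Have participants complete the adherence VAS, MOS-HIV, Patient Reactions Assessment, drug-use-days items, satisfaction form and SUMI themselves in Qualtrics on the on-site assessment computer, which is already used at the monthly visit for the MEMS reading. Switch remote viewing off during completion, and keep the student investigator available by phone for technical help only. Specify a mode for assessments done at home.

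The cost is revised manual wording and a single recording of the question audio; recorded audio is already used for consent. No extra assessor is needed. Some participants will need help with the computer, and a few more items may be skipped.

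The section on analyses for future publication is written in the past tense, so data may already be in hand. In that case, report the mode actually used at each visit, and label the self-report and acceptability results as collected by unblinded intervention staff.

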The [Addiction Severity Index-Lite](#) which assesses drug use and related problem severity

The [Patient Reactions Assessment](#) is a 15-item validated instrument for assessing a patient's perceived ability to initiate communication about their illness. This will allow us to determine whether the consult element of SteadyRx has an effect on patient's perceptions of the quality of their communication with their provider.

After the intake interview is completed, the staff member should review and complete [the Inclusion/Exclusion checklist](#). If the participant is eligible, then he/she should be informed that he/she is a candidate for diversion to treatment and he/she is invited to participate in a research study.

Any participant who is ineligible should be informed that they are not eligible to participate in the study. Upon notification of ineligibility, some participants may be saddened or angered. See the section on study eligibility for further details describing how to handle ineligible participants. Be sure to retain all completed assessments, independent of whether a participant was eligible for the study. Assessments completed by ineligible participants will be collected and stored separately from assessments completed by eligible participants.

**CD4 counts and HIV-1 RNA levels.** The participants will sign a separate consent form granting their care provider (i.e., Comprehensive Care Practice) permission to share their test results with the study team. Thus, we anticipate that we will have a baseline measure and two study period measures of [CD4 and HIV-1 RNA levels](#) for pilot study participants. We will also maintain a record of scheduled appointments and whether the participant attended each appointment (Y/N; coded yes for any appointment attended within one week of the originally scheduled date). Importantly, we will be collecting our monthly assessments on the same day as the patient is scheduled to have their CD4 and HIV-1 RNA levels checked in the same building. Note that we do not plan to interface directly with

the existing medical records systems used by care providers. Instead, care providers will submit the information to the outreach coordinator, who will relay the information to the study team in Kalamazoo via the phone.

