“You have been assigned to the control group. This means that you are able to be paid \$30 each month for coming here and completing an interview with our outreach staff. Each month, we’ll set up an appointment for the following month and our outreach staff will be calling you from time to time to remind you about your appointments and the money you can make. You will be provided with a medicine cap that will go on top of your prescription HIV medication. Each time you bring the medicine cap to an assessment interview, we will pay you \$20. We will make an appointment with you for our next meeting today before you leave. I’d also like to provide you with \$50 for coming here today, and you may also have two bus tokens if you’d like. Do you have any questions?”

If the participant was found ineligible for the study due to answers given in the ASI-Lite, then the student investigator will read the following script:

“Unfortunately, you did not qualify for the study. The good news is that we are paying you \$50 for your time today. [name] should be down any moment with the card. We want to emphasize that we thank you for coming out and taking time to complete these assessments. This also is a very important part of our study. We also wanted to note that this will not change your care at the CCP or at Johns Hopkins. Thank you again for your time.”

**MEMS Cap.** All participants will receive a MEMS cap which is to be placed on the cap of their prescription HIV medication. The intake assessment cannot take place if the participant did not bring their pill bottle. The student investigator is responsible for initiating a participant into the MEMS database located at <http://www.mwvaardex.com/>. The student investigator should use their own personal login information to access the database.

**Assigning Materials.** All participants will be assigned a CTPayer card which will be loaded with \$50 for completing the intake assessment, regardless of study group assignment. All participants will sign a SteadyRx Material Acknowledgement Form that specifies what materials they received. A log will also be updated with this information.

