adherence. Full medication adherence for the day is defined as one accepted video for the OnePerDay group in the allotted dose time window or two accepted videos for the TwoPerDay group in the allotted dose time windows.

A \$6 bonus credit should be given for full medication adherence three days in a row. At the end of every 30-day study period, each participant that has at least 29 days of full medication adherence should be credited \$20. The first two times that a participant has an undetectable viral load at their appointment with their primary care physician at CCP, they will receive an incentive bonus of \$100. All bonus credits should be manually entered into the client's account information via the client's tab in Motiv8. This includes the intake and monthly assessment payments. The student investigators will specify the reason in addition to the amount in order for the client to have a full record.

Only when the participant is due more than \$10 will the student investigators credit their CTPayer card.

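### The $100 undetectable-viral-load payment appears in both the all-participant and the SteadyRx-only procedures, with different triggers, so the manual does not settle whether controls are paid for a result tied to a primary outcome

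*Combined protocol and SAP*

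**What the plan says.** The Overview of General Procedures sets the scope of what follows: "This section on general procedures covers procedures that are applied to all randomized participants, independent of their group assignment". It adds: "The subsequent sections apply only to participants who have been assigned to the SteadyRx group".

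Within General Procedures, under Conducting Monthly Assessments, the manual says: "If the participant brought in recent CD4 and RNA lab readings and have an undetectable viral load, they should be paid" $100, up to twice in the study. No arm is named. A few lines later the same section does limit two questionnaires to the SteadyRx arm.

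Under Main Study: SteadyRx Procedures, in Assessing Videos in SteadyRx, the bonus is listed beside the video credits: "The first two times that a participant has an undetectable viral load at their appointment with their primary care physician at CCP", a $100 bonus is due. Nothing there requires the participant to bring a lab report.

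On sources of viral load, the intake section on CD4 counts and HIV-1 RNA levels says that "care providers will submit the information to the outreach coordinator", under a separate consent. Monthly Assessments makes retrieval from the medical record a coordinator duty, but also accepts printed labs that participants hand over.

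Viral load below 400 is the second primary outcome.

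**The concern.** Staff cannot tell from the manual whether a control participant with an undetectable result is owed $100, or whether the participant must bring the report to be paid. Randomization Variables calls the comparator usual care. The physician's script under Identifying Participants says that only some participants are paid for taking medication. The coordinator's recruitment script and the monthly reminder script put the pay common to everyone at $50 a month. Paying controls for an undetectable result fits poorly with all of these.

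If controls are paid, the trial compares SteadyRx with usual care plus a viral-load incentive, which is a different question for both primary outcomes and for the ICER. There is a second, smaller issue. A payment that requires a favourable report to be brought in rewards selective submission, and the same printed reports are an accepted source for the outcome.

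**Working it through.** **1. The two rules side by side**

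| | Monthly Assessments | Assessing Videos in SteadyRx |
|---|---|---|
| Scope, from the General Procedures Overview | both arms | SteadyRx only |
| Amount | $100, up to twice | $100, first two times |
| Trigger | labs brought in and undetectable | undetectable at the clinic appointment |

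Amount and cap agree. Scope and trigger do not.

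**2. Size of the incentive contrast**

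Assessment pay is the same in both arms: intake plus six monthly visits, 7 × $50 = $350.

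SteadyRx adherence credits, at most, over 180 days:
- daily credit: 180 × $2 = $360
- three-day bonus: 180/3 = 60 non-overlapping runs, 60 × $6 = $360
- 30-day bonus: 6 × $20 = $120
- total: $840

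The viral-load bonus is at most 2 × $100 = $200. The SteadyRx phone payment of $100 (or the phone itself) is left out.

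- Bonus in both arms: a control participant can earn $350 + $200 = $550, and the contrast is $840.
- Bonus in SteadyRx only: a control participant can earn $350, and the contrast is $840 + $200 = $1,040. The bonus is 200/1,040 = 19% of it.

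**3. ICER**

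The plan divides the costs of the intervention by the between-group difference in the percentage reaching 95% adherence. If only SteadyRx is paid, up to $200 per SteadyRx participant belongs in the numerator. If both arms are paid, only the difference between arms in bonuses earned is incremental. The plan does not say which applies.

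**4. When capture could bias the comparison**

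Let p be true suppression, and let c_s and c_n be the probabilities that a suppressed and an unsuppressed result reach the study.
- Missing counted as failure (the primary rule in the analytic plan): observed rate = p·c_s.
- Missing left as missing: observed rate = p·c_s / [p·c_s + (1 − p)·c_n], with odds [p/(1 − p)] × (c_s/c_n).

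If c_s and c_n are the same in both arms, no spurious difference appears under either rule. For illustration, with assumed values p = 0.60, c_s = 0.95 and c_n = 0.70 in both arms:
- missing as failure: 0.60 × 0.95 = 0.570 in each arm
- missing as missing: 0.570/(0.570 + 0.40 × 0.70) = 0.671 in each arm

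The level is distorted, but the difference is 0. If c_s differs between arms and there is no true effect, the failure rule shows p × (difference in c_s). Under the other rule, the odds ratio is multiplied by the ratio of the two arms' c_s/c_n. Counting missing results as failures therefore does not protect against this. The documents give no capture rates, so the size cannot be calculated.

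**The case against.** The strongest defence is that this is one bonus described twice. The amount and cap match, and the SteadyRx section restates other common payments when it tells staff to enter intake and monthly assessment pay. The scope sentence is itself loose, because Main Study Discharge comes later and expressly covers both arms. This shows that the two statements could coexist. It does not say whether controls are paid, and the triggers still differ.

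On capture, the defence is largely right. The record is the coordinator's stated source, the provider route has its own consent, and Data Management also says that viral load comes from the doctor. Bringing labs governs the payment under one rule; it does not govern collection as a whole. What remains is the risk where printed labs fill gaps in the record.

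Three stronger readings are tempting and are not supported:
- A reader might infer that SteadyRx participants could collect under both rules, $400 in all. That would breach the cap of two payments across the study in Monthly Assessments.
- A reader might take the control script's silence as proof that controls are unpaid. That script mentions the cap payment ("Each time you bring the medicine cap to an assessment interview, we will pay you" $20) and no viral-load bonus. The SteadyRx script mentions the phone ("If you keep your cell phone for the whole study, you will receive" $100) and no viral-load bonus either, so the silence does not separate the arms.
- A reader might link the payment rule to the biometric collection error that removed these analyses from the planned publication. The documents make no such link. The omission does mean that any capture bias would not reach the results reported there.

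**Conclusion.** The inconsistency stands: one payment, two scopes and two triggers. Under the General Procedures wording, controls are paid up to $200 for an undetectable result, which counts as success on the second primary outcome provided the assay's detection limit is no higher than 400 (not stated). The maximum contrast is then $840 rather than $1,040, given non-overlapping three-day runs and no phone payment.

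Selective capture is a risk of unknown size. It biases the arm comparison mainly if the incentive differs by arm.

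A reader might want to attach a figure in percentage points, but none can be defended. For example, assume 70% suppression in both arms, with capture of 90% of suppressed and 60% of unsuppressed results in a paid arm and 75% of all results in an unpaid arm. Missing as failure gives 63% v 52.5%; missing as missing gives 0.63/(0.63 + 0.18) = 77.8% v 70%. Changing only the 60% to 75% gives 0.63/(0.63 + 0.225) = 73.7% v 70%, so the gap falls from about 8 points to 3.7. Every rate is assumed. The scenario also joins the bring-your-labs trigger of one rule to the single-arm scope of the other, which neither rule as written does.

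**What to change.** - Reconcile the General Procedures Overview, Conducting Monthly Assessments and Assessing Videos in SteadyRx into one payment rule that names the arm or arms paid and gives a single trigger. Remove the duplicate.
- Take viral load, for both the payment and the outcome, from the provider's record for every participant in both arms, whatever the result. Do not use participant-supplied labs as an outcome source unless they are confirmed in that record.
- Make the description of control match. If both arms are paid, call it usual care plus a viral-load incentive and count the payment in both arms' costs. If only SteadyRx is paid, keep usual care and count the bonus as intervention cost in the ICER.

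The cost is manual wording, since consent for the provider to share results is already planned. The one downside is that a few results available only as printed labs may be lost or need confirmation.
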